#### Introduction

It is well-known that a small percentage of patients will have epithelial ingrowth after primary LASIK and that preoperative refractive error is a correlated factor. The effects of that ingrowth can be glare and halos; ingrowth is a significant cause of dissatisfaction after LASIK. The incidence of epithelial ingrowth is significantly higher after flap re-lift for treatment of residual refractive error. It has been hypothesized that cell migration into the flap/cornea interface postoperatively is a primary reason for such ingrowth. A sealed interface may therefore have some utility in preventing epithelial ingrowth after flap re-lift.

The following investigator-initiated study proposal is designed to determine if a lower-than-typical rate of epithelial ingrowth occurs when a LASIK flap re-lift is performed and the replaced flap is sealed with ReSure sealant.

**Study specific aims:** Tissue sealant has been effectively used to prevent recurrence of epithelial ingrowth under the LASIK flap. The aim of the study is to see if tissue sealant can be used to prevent epithelial ingrowth from occurring in the first place. This would allow for patients to undergo LASIK flap lift surgery with greater safety.

**Unpublished data:** There is no unpublished data on the prophylactic use of tissue sealant to prevent the occurrence of epithelial ingrowth under the flap. It has been used successfully to prevent recurrence of epithelial ingrowth under the flap.

#### Study design and data analysis

The study will be designed as a single-arm prospective trial involving 25 eyes (of up to 25 subjects) who are presenting for LASIK retreatment. Sample size was calculated based on a nominal historical population rate of 25% ingrowth after re-lift, and an expected rate with ReSure of 5%, using an alpha of 0.05 and a power of 0.8; with these parameters a sample of 25 eyes should be sufficient to show the expected difference.

The study will involve 5 visits per eye, including a preoperative visit. Other visits will be the operative day, and 1 day, 1 week, 1 month and 3 month postoperative visits. The primary endpoint will be presence of epithelial ingrowth at 1 and 3 months after the retreatment.

Secondary endpoints will include change in refraction, best-corrected visual acuity and uncorrected visual acuity.

Inclusion criteria will be those patients who are presenting for LASIK flap re-lift and re-ablation after initial LASIK surgery. If a surgery occurs where there are intra-operative or immediate post-operative complications unrelated to the sealant the subject may be excluded from the analysis and replaced with an alternate. The data for that patient will be retained and the affected patient will be followed to monitor for adverse events, but their outcomes data would not be included in any aggregate analysis. At each visit subjects will be monitored for adverse events, whether related to the protocol regimen or not.

**Significance:** Late flap lift enhancements are associated with a higher rate of epithelial ingrowth under the flap margin. Many surgeons have stopped performing late flap lift LASIK enhancements and switched to PRK to avoid this complication. PRK over previous LASIK is associated with a prolonged visual recovery and short term ocular discomfort. If the tissue sealant is effective at preventing or lowering the rate of epithelial ingrowth under the flap, then late LASIK flap lift treatments could be offered with greater safety. This would benefit patients.

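### Eyes with current or past ingrowth are not excluded and any ingrowth present counts as an event, so the primary rate could mix first occurrence with persistence or recurrence

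*Combined protocol and SAP*

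**What the plan says.** The Introduction gives the aim under its study-specific aims: "The aim of the study is to see if tissue sealant can be used to prevent epithelial ingrowth from occurring in the first place". The sentence before it treats recurrence as a separate use that already works: "Tissue sealant has been effectively used to prevent recurrence of epithelial ingrowth under the LASIK flap". The note on unpublished data repeats this ("It has been used successfully to prevent recurrence of epithelial ingrowth under the flap") and says there are no such data on prophylactic use.

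The section on study design and data analysis sets one entry criterion: "Inclusion criteria will be those patients who are presenting for LASIK flap re-lift and re-ablation after initial LASIK surgery". It names no exclusion at entry. The only removal from analysis concerns surgical complications unrelated to the sealant. A preoperative visit is planned, but no assessment of ingrowth is described for it. The endpoint is defined as follows: "The primary endpoint will be presence of epithelial ingrowth at 1 and 3 months after the retreatment". The comparison is with a "nominal historical population rate of 25% ingrowth after re-lift"; the make-up of that population is not described.

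**The concern.** The distinction between first occurrence and recurrence is the stated reason for the trial, but neither the entry criterion nor the endpoint carries it through. An eye that needs refractive retreatment and also has, or has had, ingrowth qualifies. If ingrowth is there at 1 or 3 months, it counts, whether it is new, left over or back again. Without a recorded baseline status, the three cannot be told apart afterwards.

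The Introduction itself says that "a small percentage of patients will have epithelial ingrowth after primary LASIK", and everyone in this trial has had primary LASIK, so such eyes can be among those who present. With 25 eyes and no control arm, the conclusion turns on one or two events. A single event of the wrong kind could decide whether the sealant appears to work.

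**Working it through.** **Inputs from the plan.** Reference rate p0 = 0.25, expected rate p1 = 0.05, alpha 0.05, power 0.8, 25 eyes, single arm. Sidedness, test and success rule are not stated.

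**The plan's own figure.** For one proportion, n = [(z_alpha·√(p0(1−p0)) + z_beta·√(p1(1−p1))) / (p0−p1)]².
- One-sided: n = 20.06. With continuity correction, (20.06/4)·(1 + √(1 + 2/(20.06 × 0.20)))² = 24.8, so 25 eyes.
- Two-sided without correction: 26.6, so 27 eyes.

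The stated 25 is therefore reproducible and is not in dispute.

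**Success rule.** For X ~ Binomial(25, 0.25), P(X ≤ 2) = 0.032 and P(X ≤ 3) = 0.096. The exact one-sided 0.05 rule is thus at most 2 events. At a true rate of 5%, power is P(X ≤ 2) = 0.873.

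**Effect of eyes with earlier ingrowth.** Let k of the 25 eyes have current or past ingrowth, and let each show ingrowth at follow-up with probability q; the others stay at 5%. The documents give neither k nor q, so both are assumptions.

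For k = 1, power = (1−q)·P(X₂₄ ≤ 2) + q·P(X₂₄ ≤ 1) = (1−q)·0.8841 + q·0.6608.

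For k = 2, power = (1−q)²·P(X₂₃ ≤ 2) + 2q(1−q)·P(X₂₃ ≤ 1) + q²·P(X₂₃ = 0) = (1−q)²·0.8948 + 2q(1−q)·0.6794 + q²·0.3074.

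| k | q = 25% | q = 50% | q = 100% |
|---|---|---|---|
| 0 | 0.873 | 0.873 | 0.873 |
| 1 | 0.828 | 0.772 | 0.661 |
| 2 | 0.777 | 0.640 | 0.307 |

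One such eye takes power below the planned 0.8 if its rate is 50% or more. Two do so at all three rates.

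**The opposite direction.** Suppose the sealant does nothing for first occurrence (25%) but holds eyes with earlier ingrowth at 5%. For k = 2, the chance of at most 2 events is 0.95²·0.0492 + 2·0.05·0.95·0.0116 + 0.05²·0.0013 = 0.046, against 0.032 with none. It stays under 0.05.

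**How likely is k ≥ 1?** Suppose each eye independently has probability π of earlier ingrowth (assumed). The chance of at least one in 25 is 1 − (1−π)²⁵: 40% at π = 2% and 72% at π = 5%. Averaged over k, each eye's event rate is (1−π)·0.05 + π·q:

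| π | q = 25% | q = 50% | q = 100% |
|---|---|---|---|
| 1% | 0.86 | 0.85 | 0.82 |
| 2% | 0.85 | 0.82 | 0.75 |
| 5% | 0.81 | 0.73 | 0.55 |

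**The case against.** The strongest reply is that such eyes will be rare. Entry requires re-ablation as well as re-lift, so a re-lift done only to clear ingrowth does not qualify; the setting is retreatment of residual refractive error; and the plan calls ingrowth after primary LASIK uncommon. This stands. At an assumed prevalence of 1%, average power stays at 82% or more whatever those eyes do. At 2% it falls below 80% only if nearly all of them fail, which sits badly with the plan's statement that sealant works against recurrence. Three or more such eyes would be an unlikely extreme (1.3% at a prevalence of 2%).

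A reader might infer that the primary rate does mix the two outcomes. The text permits this but does not show that it will happen.

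A reader might also infer that a positive result could merely reflect the known effect on recurrence. That needs a sealant that works on recurrence and not at all on first occurrence. The Introduction describes one mechanism, cell migration into the interface, and gives no reason for the effects to part. At an assumed prevalence of 5%, false success rises only from 3.2% to 4.1%.

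Finally, the Introduction also asks whether the ingrowth rate after a sealed re-lift is lower than typical, and the presence of ingrowth fits that question. First-time prevention could be read as prophylaxis at the re-lift. So it goes too far to say that the trial cannot answer its question. What remains is that the plan contrasts prevention with recurrence and then gives no means of separating them.

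**Conclusion.** The concern holds in a limited form: as written, the plan could score persistent or recurrent ingrowth as a failure of first-time prevention. The main risk is failing an effective sealant. One eye with earlier ingrowth lowers power from 87% to between 83% and 66%, and two lower it to between 78% and 31%, for assumed rates of 25% to 100% in those eyes. Inflation of false success is minor: 3.2% to 4.6% with two such eyes.

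These figures rest on a derived one-sided limit of 2 events in 25, on a 5% rate in the other eyes, and on assumed counts and rates. If 0.025 were placed in the lower tail instead, the limit would be 1 event and power 64% even with no such eyes. The direction of any bias against the 25% reference is unknown, because its make-up is not stated. The sample size calculation is not called into question. This is a cheap improvement worth making before enrolment, not a flaw that stops the trial.

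**What to change.** - Record current and previous ingrowth in the study eye at the existing preoperative visit, and make either one an exclusion at entry, settled before enrolment.
- Define the primary endpoint as new epithelial ingrowth.
- If ingrowth is first seen at flap lift, keep the eye in the study, report it separately, and show the comparison with 25% both with and without it. This avoids adding a discretionary exclusion during surgery.
- State whether the 25% historical rate includes eyes with earlier ingrowth.

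**Cost.** An eligibility sentence, a change to the endpoint wording, and a baseline ingrowth check that the plan does not now describe, made at a visit already scheduled. The 25 eyes and the calculation behind them are unchanged. A few presenting eyes become ineligible. If the historical rate does include eyes with earlier ingrowth, leaving them out of the trial alone tilts the comparison slightly toward the sealant, and the report should say so.

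### Sealed eyes with early complications may be dropped and replaced at discretion, with no deadline before the 1- and 3-month ingrowth results

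*Combined protocol and SAP*

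**What the plan says.** All but one of the relevant statements are in the section Study design and data analysis.

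- **Design and comparator.** The study is a "single-arm prospective trial involving 25 eyes". Sample size rests on a "nominal historical population rate of 25% ingrowth after re-lift" against an expected 5% with the sealant, "using an alpha of 0.05 and a power of 0.8". Neither the test nor its sidedness is named.
- **Endpoint.** Ingrowth is assessed at 1 and 3 months. The follow-up schedule is "1 day, 1 week, 1 month and 3 month postoperative visits".
- **Exclusion rule.** It is triggered by an intra-operative or immediate post-operative complication and reads: "complications unrelated to the sealant the subject may be excluded from the analysis and replaced with an alternate".
- **Excluded subjects.** Their records are kept and safety follow-up continues. On efficacy, the plan states that "their outcomes data would not be included in any aggregate analysis".
- **Timing of sealant.** The Introduction describes the procedure as one in which "the replaced flap is sealed with ReSure sealant". Sealing therefore belongs to the operation, and an immediate post-operative complication would normally occur in an eye already sealed. This is an inference from the two sections; no single sentence states it.

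The plan does not say who judges relatedness or by what criteria, by when the exclusion must be decided, or how many eyes may be replaced. It describes no masking and plans no analysis of all sealed eyes.

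**The concern.** The trigger must be early, but the decision to exclude need not be. Nothing prevents it from being taken after the 1- or 3-month ingrowth result is known. Whether a complication is unrelated to a product applied in the same operation is a matter of judgement, and nothing requires the person judging to be unaware of ingrowth status.

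There is no concurrent arm to which the same exclusions would apply, so any selection passes straight into the comparison with 25%. There are two routes to bias:

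- **Different risk.** If complicated eyes have more ingrowth than the rest, dropping them lowers the observed rate even when the decision ignores the outcome. If they have less, the rate is pushed up. If risk is equal and the outcome is ignored, there is no bias.
- **Outcome-informed choice.** If eyes with ingrowth are more likely to be excluded, the rate falls even when complicated eyes carry no extra risk.

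The study's stated aim concerns ingrowth when a flap is re-lifted and sealed, and a sealed eye with a complication belongs to that population. Because excluded outcomes are kept out of every aggregate, the reported results could not show that selection had occurred.

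**Working it through.** **Inputs from the plan:** n = 25, null rate 25%, expected rate 5%, alpha 0.05, power 0.80. **Assumed, because the plan gives nothing:** an exact binomial test; a share q of eyes with a qualifying complication of 4%, 8% or 12%; a risk ratio RR for ingrowth in those eyes of 0.5, 1, 2 or 3; and a true rate of 25% across all eyes, complicated ones included.

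**1. The plan's sample size.** By the normal approximation, one-sided:

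n = [(1.645·√(0.25·0.75) + 0.842·√(0.05·0.95)) / 0.20]² = 20.06

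With continuity correction, (n/4)·[1 + √(1 + 2/(n·0.20))]² = 24.80, that is 25 eyes. The two-sided version without correction gives 26.63 (27 eyes). The stated 25 is therefore reproduced by a one-sided, continuity-corrected calculation.

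**2. Success thresholds in 25 eyes, exact binomial.**

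- One-sided 0.05: P(X ≤ 2 | 25, 0.25) = 0.0321 and P(X ≤ 3 | 25, 0.25) = 0.0962, so success means at most 2 ingrowths.
- Two-sided 0.05 (lower tail 0.025): P(X ≤ 1 | 25, 0.25) = 0.0070, so success means at most 1.

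**3. One excluded ingrowth eye restored.**

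- One-sided: 2/25 (p = 0.0321) becomes 3/26 (p = 0.0802), and success is lost.
- Two-sided: 1/25 (lower tail 0.0070) becomes 2/26 (0.0258), just above 0.025. A minimum-likelihood two-sided p for 2/26 is 0.041, which would still pass.

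**4. False-success chance at a true overall rate of 25%.** The risk in uncomplicated eyes is x = 0.25/[1 + q(RR − 1)].

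- If every complicated eye is dropped whatever its outcome, the analysed rate is x.
- If only complicated eyes with ingrowth are dropped, the analysed rate is (1 − q)x/(1 − q·RR·x).

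The entries are P(X ≤ 2) and P(X ≤ 1) in 25 eyes at that analysed rate.

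| Exclusion | RR | q | Analysed rate | One-sided | Two-sided |
|---|---|---|---|---|---|
| Ignores outcome | 0.5 | 4 / 8 / 12% | 0.2551 / 0.2604 / 0.2660 | 2.8 / 2.5 / 2.2% | 0.6 / 0.5 / 0.4% |
| Ignores outcome | 1 | any | 0.2500 | 3.2% | 0.7% |
| Ignores outcome | 2 | 4 / 8 / 12% | 0.2404 / 0.2315 / 0.2232 | 4.0 / 4.95 / 6.0% | 0.9 / 1.2 / 1.5% |
| Ignores outcome | 3 | 12% | 0.2016 | 9.5% | 2.6% |
| Drops ingrowth only | 1 | 4 / 8 / 12% | 0.2424 / 0.2347 / 0.2268 | 3.8 / 4.6 / 5.5% | 0.9 / 1.1 / 1.3% |
| Drops ingrowth only | 2 | 4 / 8 / 12% | 0.2353 / 0.2212 / 0.2075 | 4.5 / 6.2 / 8.4% | 1.1 / 1.6 / 2.25% |

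Worked example (q = 12%, RR = 2): x = 0.25/1.12 = 0.2232. The outcome-driven rate is 0.88 × 0.2232/(1 − 0.24 × 0.2232) = 0.1964/0.9464 = 0.2075.

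Ten of these scenarios bias the rate downward. Five of them exceed 5% one-sided, and one exceeds 2.5% two-sided.

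**5. How often such an eye would arise.** The chance that at least one of 25 eyes has both a complication and ingrowth is 1 − (1 − q·RR·x)^25. At a true 25% it runs from 22% (q = 4%, RR = 1) to 75% (q = 12%, RR = 2). At the plan's expected 5%, with x = 0.05/[1 + q(RR − 1)], it runs from about 5% to 24%.

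**The case against.** The strongest reply concerns the comparator. The plan does not say whether its 25% counts eyes with surgical complications. If that figure left such eyes out, excluding them without regard to outcome would match the comparator, and an all-sealed-eyes analysis would introduce a mismatch. This stands as a limit on the outcome-blind rows of the table. It does not excuse exclusions made with the ingrowth result in hand, which distort the rate under either reading.

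The sizes also rest on assumptions. The rule reaches only early complications judged unrelated to the sealant, and it is optional, so treating every complicated eye as removable gives an upper bound for each q. Half of the downward scenarios shown stay within 5% one-sided, and nine of ten stay within 2.5% two-sided. Whether one eye reverses a two-sided result depends on how the p-value is defined. All of this stands, and it limits what can be said about magnitude.

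The plan has partial safeguards too: the rule is written in advance, its trigger is early, and data are kept with adverse-event follow-up. These protect safety monitoring. The ingrowth rate still omits the excluded eyes.

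A lighter remedy is conceivable: fixed criteria, a decision before 1 month by someone unaware of ingrowth status, and a sensitivity analysis of all treated eyes. That would close the outcome-informed route, but the main result would still leave out sealed eyes.

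**Conclusion.** The concern holds. As written, the rule allows sealed eyes to be removed from the only primary comparison after their ingrowth status is known, and it bars the aggregate analysis that would reveal this. That follows from the text and does not depend on the assumed figures.

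Whether bias would occur, in which direction and how large, cannot be established from the documents. Under an exact one-sided test and a 25% rate across all eyes, false success moves from 3.2% to between 2.2% and 9.5% over the scenarios shown. Under the two-sided test it moves from 0.7% to between 0.4% and 2.6%. Near the threshold, one eye can decide the one-sided result. The rule should be changed before the study is analysed.

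**What to change.** Replace the exclusion rule with wording such as:

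> The primary analysis includes every eye in which sealant was applied. An eye may be replaced only if sealant was never applied. All sealed eyes, including those with complications, have ingrowth assessed at the scheduled 1- and 3-month visits and stay in the aggregate efficacy and safety summaries. An analysis omitting eyes with complications unrelated to the sealant is a labelled sensitivity analysis; each exclusion and its reason is recorded before the 1-month visit, and the number excluded is reported.

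It would also help to state whether the historical 25% includes eyes with complications, so that the reader can judge which analysis it matches.

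**Cost.** One paragraph of protocol text. The analysed number remains 25, because sealed eyes are no longer replaced. Power at a true 5% with 25 sealed eyes is P(X ≤ 2 | 25, 0.05) = 87.3% under the assumed one-sided test and P(X ≤ 1 | 25, 0.05) = 64.2% under the two-sided one. The current text promises adverse-event follow-up of excluded subjects but not expressly their ingrowth assessment. The new wording requires that at visits already scheduled. The downsides are that the observed rate may look slightly less favourable and that, if the 25% excluded complicated eyes, the primary comparison would be somewhat conservative should those eyes carry higher risk. The sensitivity analysis covers that case.

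### The exclusion rule lets sealant-treated eyes with complications judged unrelated to the sealant drop out of the refraction and acuity summaries, and leaves unclear whether their adverse events are counted

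*Combined protocol and SAP*

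**What the plan says.** All the relevant text is in the combined protocol and SAP, in the section on study design and data analysis.

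- **Trigger.** The rule applies to a surgery with "intra-operative or immediate post-operative complications unrelated to the sealant the subject may be excluded from the analysis and replaced with an alternate". It is optional, and it names no assessor and no criteria for relatedness.
- **What is kept.** "The data for that patient will be retained and the affected patient will be followed to monitor for adverse events".
- **What is left out.** The same sentence continues: "but their outcomes data would not be included in any aggregate analysis".
- **Monitoring.** The next sentence reads: "At each visit subjects will be monitored for adverse events, whether related to the protocol regimen or not".
- **Endpoints in reach of the rule.** "Secondary endpoints will include change in refraction, best-corrected visual acuity and uncorrected visual acuity". The primary endpoint is ingrowth at 1 and 3 months.

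The design is a single arm of 25 eyes. The section defines no all-treated set or safety population, and it describes no adverse-event summary.

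**The concern.** The rule is not confined to one endpoint. Refraction and the two acuity measures are outcomes on any reading, so an excluded eye's results leave every summary of them. The selection is made on a surgical complication that arises during or just after treatment. It is reasonable, though not shown in the documents, to expect such eyes to be at higher risk of a poor visual result. Removing them would then tilt the secondary results in the favourable direction.

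Replacement makes the loss hard to see, because the analysed count returns to 25. A single-arm design also has no control group against which to judge whether a complication was due to the sealant, so the attribution that decides who stays in rests on judgement.

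For adverse events the difficulty is ambiguity. Events are collected whatever their cause, but the plan does not say whether those of excluded subjects are ever tabulated.

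**Working it through.** **1. The plan's own figure.** The stated sample size is 25 eyes, for 25% against 5% ingrowth, alpha 0.05 and power 0.80. For one proportion against a fixed value, one-sided:

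n = [(1.645·√(0.25·0.75) + 0.842·√(0.05·0.95)) / 0.20]² = 20.1.

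With the continuity correction, n' = (n/4)·[1 + √(1 + 2/(n·0.20))]² = 24.8, so 25. The figure reproduces under that one-sided, continuity-corrected choice (the plan does not state the sidedness). The point here does not depend on it, except that 25 is the count that replacement restores.

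**2. Which data leave the summaries.** Set the clauses side by side:

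| Data on an excluded subject | Status in the text |
|---|---|
| Refraction, best-corrected and uncorrected acuity | Retained, but left out of every aggregate |
| Ingrowth | Retained, but left out of every aggregate |
| Adverse events | Monitored; inclusion in any total not stated |

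**3. Can an excluded eye have received the sealant?** Yes. An immediate post-operative complication occurs after the operation. An intra-operative one may come before or after sealing, so some excluded eyes may never have been sealed.

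**4. Illustration of size.** The documents give no rate of complications, exclusions or acuity loss. Assume 3 sealed eyes are excluded and replaced, so 25 + 3 = 28 are treated, and that none of the 25 analysed eyes loses best-corrected acuity. The exact (Clopper-Pearson) 95% limits for x events in n eyes are the 2.5% quantile of Beta(x, n−x+1) and the 97.5% quantile of Beta(x+1, n−x), with lower limit 0 when x = 0.

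| Excluded eyes with acuity loss | Reported | All sealed eyes |
|---|---|---|
| 0 of 3 | 0/25 (0 to 13.7%) | 0/28 (0 to 12.3%) |
| 1 of 3 | 0/25 (0 to 13.7%) | 1/28 = 3.6% (0.1 to 18.3%) |
| 2 of 3 | 0/25 (0 to 13.7%) | 2/28 = 7.1% (0.9 to 23.5%) |

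With no exclusions the effect is nil.

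**5. Why the remedy must not confine the exclusion to the primary analysis.** The same clause removes ingrowth results. With 2/25 ingrowths, the exact one-sided p against 25% is 0.032. If one excluded eye also had ingrowth, 3/26 gives p = 0.080. Wording that kept the exclusion for ingrowth alone would write that removal into the analysis carrying the study's claim.

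**The case against.** The case against a stronger reading is good, and most of it stands.

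- **A reader might infer that the trial would report on 25 uncomplicated eyes.** It would not. Exclusion is optional and covers only early complications judged unrelated to the sealant. Sealant-related complications, later complications and any eye the investigator chooses to keep all remain.
- **A reader might infer that adverse events of excluded subjects are lost.** The text does not say so. It sets adverse-event follow-up against outcomes data, and the natural contrast is with ingrowth, refraction and acuity. Monitoring events of all causes does not contradict leaving endpoint data out of an aggregate. What remains is silence on whether these events are tabulated.
- **A reader might take the safety conclusion to rest on these summaries.** The plan says that "then late LASIK flap lift treatments could be offered with greater safety" on the condition that the sealant prevents or lowers ingrowth. That conclusion hangs on the primary endpoint, and no safety summaries are described.
- **The illustration uses assumed counts.** That is so. One affected eye moves the upper limit only from 13.7% to 18.3%, and the direction of the bias is an expectation that the documents do not demonstrate.
- **These are secondary endpoints with no stated test.** This limits the consequence but does not remove it. The clause is an explicit instruction to omit treated eyes, and nothing else in the plan brings them back.

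**Conclusion.** The concern holds in a limited form. Followed as written, the refraction and acuity summaries may omit sealant-treated eyes chosen by a complication during or after treatment, with the count made up to 25 by replacement. This is certain from the text. That the omission flatters the visual results is likely but assumed. Whether adverse events are affected is an ambiguity to be resolved.

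The effect is zero with no exclusions. Under the assumed 3 exclusions with 1 or 2 acuity losses, an all-treated rate of 3.6% or 7.1% would be reported as none. The documents do not support saying that all complicated eyes vanish, that harms are dropped, or that every excluded eye was sealed. The change is still worth making, because it is specific, removes a source of bias and uses data the plan already keeps.

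**What to change.** 1. Delete the clause "but their outcomes data would not be included in any aggregate analysis".
2. State that adverse events, change in refraction, best-corrected acuity and uncorrected acuity are summarised over every eye that received the sealant, including excluded and replaced eyes. Deletion alone is not enough, because the preceding sentence still allows exclusion from the analysis.
3. Report the number of excluded eyes and, for each, the reason, whether sealant was applied, and final acuity.
4. Add no wording that endorses the exclusion for the primary ingrowth analysis.

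The cost is a few sentences. Data retention and adverse-event follow-up are already planned, but the sponsor must confirm that acuity (and refraction) continue to be measured at the scheduled visits in excluded eyes. The reported figures may look slightly less favourable. The sample size does not change.
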